#### Assault and Drinking Outcomes

*Alcohol Consumption (bi-weekly, all drinking occasions).* Using a grid-based average assessment measure based in the Daily Drinking Questionnaire (Collins et al., 1985), participants will report on alcohol consumption, on occasions when they were out with the target friend. See above for detailed description.

*Sexual assault (bi-weekly).* This intervention is designed to target risk for a full range of non-consensual sexual experiences, from unwanted sexual attention, to completed rape. Because lower-severity events are more frequent and may signify risk for higher severity events, it may be in lower-severity situations where there is greatest opportunity for intervention. Following Kelley-Baker (2008) for assessing assault-events for particular occasions, we will use the Revised SES to assess each social occasion with the target friend in the prior week. Each item will be coded 1(yes) or 0 (no), based on whether it happened to the woman/friend on each occasion that the pair socialized together.

*Alcohol-Related Protective Behaviors (baseline, bi-weekly).* Because one strategy women may use to decrease assault risk is to limit their own and friend's alcohol consumption, we will administer the Protective Behaviors Strategy Survey (PBSS; Martens et al., 2005).

Treatment Evaluation. (Used in Stages 2, 3; from Borsari et al., 2007)

End of Session Questionnaire. Completed at the end of the intervention session, this 6-item measure evaluates the participant's perceptions of the personal relevance of and engagement in the session. Participants also will complete a 1page survey that asks about their experiences in the session.

End of Treatment Questionnaire. This 48-item measure assesses participant perceptions of the helpfulness of each treatment component on a scale from -3 (*greatly harmful*) to +3 (*greatly helpful*). Participants will also be asked to elaborate on their perceptions of what was helpful and/or harmful (i.e., iatrogenic effects).

Therapist Assessment. (Used in Stages 2, 3)

Brief Intervention Adherence Checklist. Following prior MI studies (Barnett et al. 2007; Murphy et al., 2010), 25% of the interviews will be selected randomly for review by [name]. Two aspects will be assessed, Content and MI Adherence. [name] will complete a 52-item checklist based on the FMI components (*content*), to evaluate whether each intervention component was covered (Moyers et al., 2010), as well as the MITI (below) for each session to determine whether interventionists maintain MI proficiency.

Motivational Interviewing Treatment Integrity Code Version 3.1.1 (MITI 3.1.1; Moyers et al., 2010) The MITI evaluates interventionist adherence to MI principles. Randomly-selected 20-minute segments of the session are coded. The MITI contains global and behavior components. The global ratings are (a) evocation; (b) collaboration; (c) autonomy/support; (d) direction; (e) empathy; (f) acknowledging change talk; and (g) inviting change talk. The behavior counts assess (a) MI adherent (e.g., emphasizing self-efficacy) and MI non-adherent (e.g., confronting) behaviors; (b) the types of questions; (c) types of reflections, and (d) providing information. As the FMI is built on a MI framework, it is crucial to examine therapist interactions to evaluate the level of collaboration, empathy, and autonomy/support infused through the session interaction. As MI focuses on attaining high ratings in these areas as more predictive of behavior change (Miller & Rollnick, 2012), our ability to evaluate if and how well the therapists delivered these skills is a crucial aspect of intervention fidelity.

Relationship Quality

Effects on the relationship are among the primary concerns that women cite regarding intervening in potential assault situations. Thus, we will examine whether the intervention has any influence on the relationship quality. Further, given that relationship and responsibility are strong predictors of helping behavior, we also will examine these as potential moderators of intervention outcome in exploratory analysis.

*Relationship Quality (baseline, follow-up).* A brief 5-item version of the Network of Relationships Inventory (NRI, Furman & Buhrmester, 1985) will be used to assess relationship quality (companionship, reassurance of worth, intimate disclosure, reliable alliance, and affection). These items will be augmented with items that query about the sense of working as a team toward one another's safety, and to what extent they were supporting one another's change efforts (e.g., *"I felt like we worked together to follow our safety plans."*).

*Responsibility (Baseline, bi-weekly).* We will assess Responsibility using a 4-item measure developed by Banyard et al. (2007) that reflects taking responsibility for preventing sexual or other forms of interpersonal violence. This measure will be adapted to reflect a sense of responsibility to the target friend in the dyad.

Exit interview

Following the 12-week follow-up, women will be contacted by phone for a brief exit interview. At this time, women will be given the chance to share any last reactions to or thoughts about the intervention, to pose questions, or inquire about resources. At this interview we also will elicit ideas for application in other settings and populations, and other friend types (e.g., male friends, non-drinking friends, etc.). This

interview will give participants a chance to talk with project staff about anything that was distressing over the trial/12-weeks.

10.4 *Describe any source records that will be used to collect data about subjects (e.g. school records, electronic medical records).*

Response: N/A. No source records will be used in this study.

10.5 *Indicate whether or not individual subject results, such as results of investigational diagnostic tests, genetic tests, or incidental findings will be shared with subjects or others*

Response: No individual results will be shared with participants or others.

10.6 *Indicate whether or not study results will be shared with subjects or others, and if so, describe how these will be shared.*

Response: Study results will be shared with participants on our study website, as they are available.

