**Stage 3 Procedures:**

*Intervention: FMI Mini-Controlled Trial with Intensive Follow-Up*

In this stage, we will test the finalized FMI (see **Screening, Eligibility, and Recruitment** above). To do this, we will contrast outcomes among those in this trial (N=24 dyads) with 24 pairs of friend dyads (total dyad N=48) who are randomly assigned to a wait list control condition.

The FMI will consist of a single session. Sessions will be offered on many days and times across the week to accommodate variability in student schedules. Each session will begin with a baseline assessment. In this session, women will be provided with the refined intervention protocol and will have the opportunity to role play and practice implementing the skills and strategies. Following the intervention, participants will be encouraged to utilize the skills and strategies presented in the intervention over the next 12 weeks, whenever they are out with their friend in a social context.

Dyad pairs assigned randomly (stratified on drinking levels, sexual assault history, and age) to the wait list control condition will be assessed once at baseline and again 12 weeks post-baseline. Assessment measures (baseline, 12 weeks) will mirror those administered to women in the FMI condition. At the completion of the 12 week “wait list,” participants will be administered the FMI and followed for 12 weeks. Comparison of outcomes across conditions will allow for stronger inferences about the efficacy of the intervention, will allow for examination of measurement reactivity, and will increase our sample size to examine within person change.

*Follow-up Assessments.* We will conduct bi-weekly online post-intervention assessments (with the first assessment to occur within 2 weeks of FMI completion) for 12 weeks. The bi-

weekly structure will optimally capture women's experiences applying strategies from the intervention. Participants will be reminded of follow-up assessments by phone, text, and email prompt. Individual members of the dyad will be interviewed in the unlikely event that the other member is lost to follow up over the brief follow-up period. At the end of the 12 weeks, participants will be contacted for an exit interview.

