*Stakeholder interviews.* In this second set of stakeholder interviews, we will gather information to inform next steps for the FMI intervention. To this end, a series of 5 interviews (2 randomly selected from prior interviews, 3 new to the project) will be conducted with campus administrators at Buffalo-area colleges. Selection will follow procedures outlined in Stage 1. In these interviews, the final FMI manual will be presented, and feedback would be solicited regarding ideas for scaling the FMI to other populations and contexts.

*Remuneration.* Students will receive electronic gift card payments of \$40 for the baseline assessment (which occurs just prior to the intervention) and \$20 for each post-intervention assessment. To encourage participant retention, participants who complete at least 4/6 bi-weekly assessments will receive a \$20 bonus. Stakeholders will receive \$25 in cash as a gesture of appreciation for participation.

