#### **Bi-Weekly Follow-Up Assessment**

**Overview:** Bi-weekly, participants will report on any occasion since the last assessment that the participant was out with the target friend in a social setting. For each such occasion, we will collect information about the context of these occasions (i.e., bar, party, out to dinner), whether there was alcohol, who was present, and whether there was an opportunity for intervention.

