A prominent feature of our design is that individuals are nested within dyads, and this necessitates a data analytic approach that can accommodate nested data structures. Hence, our Aim 3 analyses are built around hierarchical linear models (HLMs). First, we will evaluate group differences on variables from our first post-intervention assessment (i.e. perceived barriers, readiness, alcohol knowledge and strategies, and implementation of FAPBs) using a two level model (individuals nested within dyads). Treatment will be dummy coded (FMI vs. waitlist control group) and included as a level two covariate. Second, we will utilize all data from our three month follow-ups and repeat these analyses using a three-level model (6 repeated measures nested within individuals, and individuals nested within dyads). In these models treatment will be included as a level three covariate. We will use  $\beta$  to describe effect sizes (Cohen, 1988; Selya et al., 2012).

Our burst design provides a rich opportunity to examine whether changes in target constructs of interest (e.g., barriers, skills, alcohol knowledge and strategies) are associated with implementation of FAPBs. For these analyses we will combine the post-intervention data from our FMI and WLC groups after the latter has completed the intervention and follow-up assessments. Combining groups will increase our sample size and provide more stable estimates of effect sizes. For these analyses we will include reports of past week protective behavioral strategies just prior to the intervention and weekly aggregates of variables of interest from our three-month follow-up yielding 7 repeated measures nested within individuals and individuals nested within dyads. Time will be included as a level-1 covariate, and we will

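### The follow-up assault item has two conflicting recall windows on a two-week survey schedule, and follow-up drinking is limited to target-friend outings while the baseline it is to be compared with is not

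*Combined protocol and SAP*

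**What the plan says.** **Recall window.** In protocol section 10.3, the overview under Bi-Weekly Follow-Up Assessment says that "participants will report on any occasion since the last assessment that the participant was out with the target friend in a social setting". Under Assault and Drinking Outcomes, the sexual assault measure, itself labelled bi-weekly, says "we will use the Revised SES to assess each social occasion with the target friend in the prior week".

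**Schedule.** Stage 3 Procedures states: "We will conduct bi-weekly online post-intervention assessments (with the first assessment to occur within 2 weeks of FMI completion) for 12 weeks". The retention bonus goes to those who "complete at least 4/6 bi-weekly assessments". The SAP's three-level model uses "6 repeated measures nested within individuals, and individuals nested within dyads". Its pooled analysis uses "weekly aggregates of variables of interest from our three-month follow-up yielding 7 repeated measures nested within individuals". Weekly wording also appears in the Aim 3 statement, the introduction to the Stage 3 measures, the section 11.3 timeline and the pooled analysis in section 16.1.

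**Wait-list arm.** Stage 3 Procedures says that the "wait list control condition will be assessed once at baseline and again 12 weeks post-baseline". It adds: "Assessment measures (baseline, 12 weeks) will mirror those administered to women in the FMI condition".

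**Drinking.** The baseline drinking history (section 10.3) records typical weekly consumption. It has no target-friend limit, and its past-week version is said to be there for comparison with follow-up. The follow-up alcohol measure is headed as covering all drinking occasions, but its text asks only about occasions out with the target friend.

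**Coding and analysis.** Each follow-up assault item is coded yes or no according to whether it happened to the woman or the friend. The plan does not say that the two are recorded separately, although the protective-behavior measures in the same section ask about each in turn. Section 16.1 and the SAP collapse follow-up into one yes/no victimization variable per woman, without naming a recall window.

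**The concern.** The two window rules apply to the same survey and cannot both be followed. If the item is programmed with the one-week window, assaults in the other week of each interval are never collected. No modelling repairs that, because the loss is in what was asked and not in who answered. The exploratory model, which regresses victimization on the intercepts and slopes of the friend-based assault prevention behaviors, would have fewer events and less precision. For the wait-list 12-week survey the same two rules mean 1 week or 12 weeks.

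The drinking problem is different. Baseline and follow-up are meant to be compared but count different things, so a baseline-to-follow-up change mixes a change in drinking with a change in scope.

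The assault coding is a smaller point. The victimization model has individuals nested within dyads. If one code covers an event to either member, a friend's assault can enter as the respondent's own outcome.

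**Working it through.** **1. Schedule check.** 12 weeks / 2 weeks per survey = 6 surveys, as in the bonus rule and the three-level model. Adding baseline gives 7, as in the pooled analysis. A weekly schedule would give 12 and 13. So bi-weekly means every two weeks, and the one-week recall is probably left over from a weekly schedule.

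**2. Coverage.** Weeks asked = surveys × recall length.
- Since the last assessment: 6 × 2 = 12 of 12 weeks.
- One week: 6 × 1 = 6 of 12 weeks.

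**3. Illustration of captured risk.** The only rate in the documents is about 30% over 3 months (section 16.1 and SAP). It comes from a cited source and is not stated to apply to outings with the target friend. I therefore assume, for illustration, a 30% 12-week risk on the occasions asked about. With a constant hazard equal across women, the captured proportion is 1 − 0.7^(weeks asked / 12).
- 12 weeks: 1 − 0.7 = 0.300.
- 6 weeks: 1 − 0.7^0.5 = 0.163.

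If events cluster in the same women, a gamma frailty with variance t gives L = (0.7^(−t) − 1)/t, and the captured proportion at 6 weeks is 1 − (1 + tL/2)^(−1/t).

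| t | Captured at 6 weeks |
|---|---|
| 1 | 17.6% |
| 3 | 20.1% |
| 5 | 22.1% |

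**4. Precision, same assumption.** The approximate 95% confidence-limit factor for an odds ratio per standard deviation, ignoring dyad clustering, is exp(1.96 / √(N p(1 − p))). With N = 2 × 48 = 96:
- p = 0.300: exp(1.96 / √20.16) = 1.55.
- p = 0.163: exp(1.96 / √13.1) = 1.72.

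With the N of 88 given in section 16.2, the factors are 1.58 and 1.76.

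**5. Drinking, total volume.** Let V be true weekly volume, unchanged over time, and s the share drunk away from the target friend. Baseline records V and follow-up records (1 − s)V per week, so the apparent fall is s. The documents give no value for s. At an assumed 10%, 25% or 50%, the false fall is 10%, 25% or 50%.

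**6. Drinking, drinks per occasion.** Let q be the share of occasions that are friend outings, with mean m_f on those and m_o on the others. Baseline records q·m_f + (1 − q)·m_o and follow-up records m_f. The difference is (1 − q)(m_f − m_o). It can be positive, negative or zero, so the direction is unknown.

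**The case against.** The best defence on the window is that the one-week phrase is an editing remnant. The overview governs every bi-weekly measure, and the assault item's coding sentence covers each occasion the pair socialized together, with no one-week limit. The survey instruments are not in the documents, so loss of data is possible but not shown. All of this stands. It lowers the probability of loss but does not remove the contradiction, and the SAP does not choose between the rules.

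Four stronger readings are tempting, and the documents do not support them.
- A reader might infer that unequal windows would bias a comparison of assault rates between arms. Stage 3 does raise, as exploratory, whether the intervention is associated with lower assault risk. But neither section 16.1 nor the SAP contains a between-arm victimization model. The planned model uses growth terms from pooled post-intervention data. Wait-list women are also followed for 12 weeks after receiving the intervention, so the window there is the same for both groups.
- A reader might turn 30% into expected numbers of women with an event. The 30% is not tied to joint outings, so such counts would claim too much.
- A reader might say that any drinking measure must show a false fall. That holds for total volume, not for drinks per occasion, and the plan does not name the scored variable. A between-arm contrast on the same follow-up items does not have this artefact.
- A reader might see the heading of the alcohol measure as a clear conflict with its text. Read with the overview, it can mean every joint outing that involved drinking. The firm point is the mismatch with baseline.

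**Conclusion.** The point holds at moderate weight. The two recall rules contradict each other. Following the one-week rule on the six-survey schedule leaves half of follow-up, 6 of 12 weeks, unasked and unrecoverable. Under the illustrative 30% risk, captured risk would be about 16% with a constant hazard, or 18% to 22% with clustering. The consequence is reduced precision in an exploratory model.

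The baseline and follow-up drinking scopes differ although a comparison is intended. A change in total volume would carry a false fall equal to the share of drinking away from the friend, and that share is not given. Victimization is exploratory and drinking secondary, so no primary aim is affected. The reason to act is that the survey wording has to be right before the data are collected.

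**What to change.** - Use the interval since the last assessment as the recall window in both the overview and the assault item, and remove the leftover weekly wording from the Aim 3 statement, the Stage 3 measures introduction, the timeline, section 16.1 and the SAP.
- State the recall window of the wait-list 12-week survey.
- Measure drinking with the same scope at both times. Either collect all occasions at follow-up with a yes/no flag for whether the target friend was present, or add a matching friend-outing item at baseline. Compute change only on the matched measure.
- Record the respondent's own victimization separately from her report of the friend's, and use her own in the individual-level model.

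The cost is reworded items and slightly longer online surveys, with no extra visits. A full two-week window may bring more assault disclosures, and so more staff contact under the adverse-event procedures in section 20.2.

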## 11.0 Study Timelines

11.1 *Describe the anticipated duration needed to enroll all study subjects.*

Response: We expect that all study subjects will be enrolled within the first 2.5 years of the project, so by January of 2020.

11.2 *Describe the duration of an individual subject's participation in the study. Include length of study visits, and overall study follow-up time.*

Response: Once enrolled, participants will be followed over a period of 3 months.

11.3 *Describe the estimated duration for the investigators to complete this study.*

Response: See timeline, below.

Funding Period	Staffing & Training	Stage I FMI Development	Screening and Recruitment	Stage I: Focus Groups (N= 6-8 per group)	Stage 1 Review and Modification	Stage 2: Open Trial (N= 16)	Short-term Follow -Up	Stage 2 Review and Modification	Stage 3 Intervention mini-RCT (N=92) Intervention WLC conditions	3 MO FU (weekly online assmts)	Data Analysis and Report Writing
Sept '18-Dec '18	X	X									
Jan 19-Mar '19		X	X	X							
April '19-June '19			X	X	X						X
July '19-Aug '19					X						X
Sept '19-Dec '19	X		X			X	X				X
Jan '20-March '20			X			X	X	X			X
April '20-June '20							X	X			X
July '20-Sept '20	X		X						X		X
Oct 20-Dec '20	X		X						X	X	X

Jan '21- Mar '21			X						X	X	X
April '21- June '21			X						X	X	X
July '21- Aug '21										X	X

### **Setting**

**11.4** *Describe all facilities/sites where you will be conducting research procedures. Include a description of the security and privacy of the facilities (e.g. locked facility, limited access, privacy barriers). Facility, department, and type of room are relevant.*

Response: Data collection will be conducted via in person interviews and online. For online assessments, assessments will be completed by participants in their own local setting. Instructions for the online surveys will suggest to participants that they complete online surveys at a time and in a place where privacy can be ensured. In person assessments will be conducted on UB's North Campus, in [name] research lab.

#### **For research conducted outside of UB and its affiliates, describe:**

Response:

**N/A:** This study is not conducted outside of UB or its affiliates.

## **12.0 Community-Based Participatory Research**

**12.1** *Describe involvement of the community in the design and conduct of the research.*

Response:

**N/A:** This study does not utilize CBPR.

**12.2** *Describe the composition and involvement of a community advisory board.*

Response:

**N/A:** This study does not have a community advisory board.

## **13.0 Resources and Qualifications**

**13.1** *Describe the qualifications (e.g., education, training, experience, expertise, or certifications) of the Principal Investigator and staff to perform the research. When applicable describe their knowledge of the local study sites, culture, and society. Provide enough information to convince the IRB that you have qualified staff for the proposed research.*

Response: [name] work has focused on the complex intersection of trauma (including sexual victimization) and alcohol misuse. She also has examined developmental pathways to risk behaviors from early to late adolescence and into young adulthood. These studies have employed longitudinal, web-based methods such as those that will be used in the proposed study. [name] has assembled an outstanding team of investigators who are ideally suited to ensure the successful completion of this project's aims. All members bring unique and critical expertise to the project. All study staff will be well trained in research procedures, and in ethical treatment of human subjects. All members of the study will complete CITI training.

